7.1.2.5. Statistical Analyses/Methods

Hgb Efficacy Co-Primary Statistical Analyses
Endpoint(s)
Mean change in Hgb between baseline and EP
Model Specification
• Hgb during the EP will be defined as the mean of all available post-randomization Hgb values (on and off-treatment) during the EP (Week 28-52).
 The ANCOVA model used to quantify the difference in mean Hgb change will adjust for the
following baseline values:
• Treatment
 Baseline Hgb (see Section 10.5.2)
 Dialysis type (as randomized, see Section 10.10.2)
 Region (as randomized, see Section 10.9 & Section 10.10.2)
Multiple Imputation Analysis
 Multiple imputation analysis will be performed using all available Hgb values (on and off- treatment) and conducted under a set of assumptions about missing Hgb values (see Section 10.6.3).
 Intermittent missing post-baseline scheduled Hgb data in both arms through Week 52 will be imputed using PROC MI procedure with NIMPUTE = 200 and MCMC IMPUTE = monotone to generate 200 datasets with only monotone missing patterns. Burn in iterations (NBITER) and maximum iteration (MAXITER) will both be set to 500. The seed for reproducibility is set to 200807. The imputations will be done by randomized treatment, dialysis type, and region. For each of the monotone missing dataset (out of the 200 imputed as indicated above), the missing scheduled Hgb values through Week 52 will be imputed based on the MAR assumption and will be performed using PROC MI by treatment, dialysis type, and region. The monotone regression will have baseline Hgb, prior scheduled (possibly imputed) Hgb values, and may include dialysis type and region as covariates
 (see Model Checking & Diagnostics, below). The seed for reproducibility is set to 200807. The low and high cutoffs at Hgb values of 6 g/dL and 15 g/dL will be applied to all
imputed Hgb values.
 EP Hgb values will be computed and compared across treatment groups using the co- primary ANCOVA model described above. Rubin's rules [Rubin, 1987] will be used to combine results of the imputed datasets using SAS PROC MIANALYZE procedure. As a result, a single estimated treatment difference and its standard error will be produced, with which a 95% CI will be calculated.
Model Checking & Diagnostics
Refer to Appendix 12: Model Checking and Diagnostics for Statistical Analyses.
Model Results Presentation

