10.3. Appendix 3: Assessment Windows

Data for continuous variables that are not related to time-to-event will be summarized according to the scheduled visit time period for which they were recorded in the eCRF. Unscheduled assessments will not be slotted to a particular time point, but will remain as unscheduled if they are either summarized or listed unless otherwise specified (i.e. Hgb endpoints described in Section 10.6.3 and BP endpoints described in Section 10.6.4).

200807

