10.6.3. Efficacy

10.6.3.1. Hemoglobin Endpoints

Не	moglobin Values		
Ce	ntral Laboratory and HemoCue Hgb Values		
•	 When source of Hgb measurement is not specified: For reporting purposes, central laboratory Hgb values will be used, unless otherwise specified. However, if a central laboratory Hgb value is missing, a corresponding non-missing HemoCue Hgb value will be used. This approach will be used for the co-primary Hgb analysis. 		
•	Some displays may be created for either central laboratory Hgb values only or HemoCue Hgb values only. The central laboratory summary will be considered the primary summary in this case.		
Ev	aluable Hemoglobin Values		
•	Evaluable Hgb values are on-treatment Hgb values (see Section 10.4.1) that are not taken within the 8 weeks following a red blood cell transfusion, a whole blood transfusion, or a non- randomized ESA treatment which occurs on or after the randomization date. Red blood cell transfusions, whole blood transfusions and non-randomized ESA treatments occurring on or after the randomization date are identified by comparing the start and stop date of the respective transfusion or ESA concomitant medication record to the randomization date.		
Im	Imputed Hemoglobin Values		
•	For each missing value between baseline to Week 52 (inclusive), 200 imputed values will be generated using the multiple imputation method (see Section 7.1.2). The average of these 200 imputed values will be used as the value for this missing value in the summary tables and figures.		

He	emoglobin V	alues				
•	For co-primary efficacy Hgb analysis and the corresponding subgroup analyses using all available observed and imputed Hgb values (on and off-treatment), Rubin's rules [Rubin, 1987] will be used to combine results of the imputed datasets using SAS PROC MIANALYZE procedure.					
EF	[•] Hemoglobi	n Value for Co	p-primary Hg	b Analysis		
•	(See Section during this Should the	on 10.6.1) inclu time period. assessment da	ding any impu ates for Hgb v	uted and unsch alues from the	treatment) Hgb values neduled Hgb values that Early Treatment Disco	t were taken ntinuation visit
					e values will be include ot be included in the EF	
EF	-	-			ble Hgb Supportive Ar	

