•	For each su including an Should the and the En	ubject, the meany evaluable ur assessment da d of Study visit	n of all evalua nscheduled H ates for Hgb v fall within the	able Hgb value gb values that alues from the EP, then thes	es during the EP (See S were taken during this Early Treatment Disco e values will be include	ection 10.6.1) time period. ntinuation visit d as unscheduled
	-				ot be included in the EF	^o mean.
EF	•	n Value for Al			2	
•	 For each subject, the mean of all Hgb values during the Alt. EP (See Section 10.6.1) including any imputed and unscheduled Hgb values that were taken during this time period. This analysis will be conducted using all available (on and off treatment) Hgb values and separately using evaluable Hgb values only. Should the assessment dates for Hgb values from the Early Treatment Discontinuation visit and the End of Study visit fall within the Alt. EP, then these values will be included as unscheduled Hgb values. Hgb values from the Follow-up visit will not be included in the Alt. EP 					
	mean.					
Us	se of Unsche	duled Hemog	lobin Values	and Multiple	Hgb Values on the Sa	me Date
•						
	co-primary Hgb analysis, where central lab values are used if they are available and if the central lab value is missing, then a corresponding non-missing HemoCue Hgb value is used.					
•		ning scenarios i /pe apply to all	-		heduled and unschedu	led Hgb values of
	Scheduled Central Lab Hgb Value	Unscheduled Central Lab Hgb Value	Scheduled HemoCue Hgb Value	Unscheduled HemoCue Hgb Value	Value to Use	Type/Label
	X				Scheduled central lab Hgb value	Scheduled visit
		х			Unscheduled central lab Hgb value	Unscheduled
			х		Scheduled HemoCue	Scheduled visit
					Hgb value Average of scheduled	

200807

			х	Unscheduled HemoCue Hgb value	Unscheduled	
	multiple			Average of unscheduled central lab Hgb values	Unscheduled	
			multiple	Average of unscheduled HemoCue Hgb values	Unscheduled	
х	x			Average of central lab Hgb values	Scheduled visit	
х		Х		Scheduled central lab Hgb value	Scheduled visit	
Х			х	Scheduled central lab Hgb value	Scheduled visit	
	х	Х		Unscheduled central lab Hgb value	Unscheduled	
	x		х	Unscheduled central lab Hgb value	Unscheduled	
		X	x	Average of HemoCue Hgb values	Scheduled visit	

Time In Range

Time in Range During the EP

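### One row of the same-date hemoglobin table labels the result Unscheduled although a scheduled HemoCue was taken that day, so a measured visit is imputed; the effect is very small

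*SAP*

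**What the plan says.** **Choice of source.** SAP Section 10.6.3.1 puts the central laboratory first. For reporting, and expressly for the co-primary analysis, "if a central laboratory Hgb value is missing, a corresponding non-missing HemoCue Hgb value will be used".

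**Same-date table.** The same section lists combinations of scheduled and unscheduled, central and HemoCue values on one date, and gives a value and a label for each. Three rows matter here:

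- Scheduled central with unscheduled central: "Average of central lab Hgb values Scheduled visit".
- Scheduled HemoCue with unscheduled HemoCue: "Average of HemoCue Hgb values Scheduled visit".
- Unscheduled central with scheduled HemoCue: "Unscheduled central lab Hgb value Unscheduled".

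The third outcome also appears for an unscheduled central value alone and for an unscheduled central value with an unscheduled HemoCue. In those two rows nothing scheduled was measured, and the label is right.

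**Imputation.** Section 7.1.2.5 works on scheduled values in both steps. First, "Intermittent missing post-baseline scheduled Hgb data in both arms through Week 52 will be imputed using PROC MI procedure"; then "the missing scheduled Hgb values through Week 52 will be imputed based on the MAR assumption". Its summary of imputed data counts unscheduled evaluation-period values separately from the seven scheduled ones.

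**Slotting.** Appendix 3 (Section 10.3) says "Unscheduled assessments will not be slotted to a particular time point" unless otherwise specified, and names the hemoglobin endpoints of Section 10.6.3 as such an exception. For this combination Section 10.6.3.1 keeps the label Unscheduled.

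**Evaluation-period mean.** Section 10.6.3.1 averages each subject's values over the period and includes both imputed and unscheduled values.

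**The concern.** A subject who attends a scheduled visit and has only the scheduled HemoCue keeps that visit as observed. If the same subject also has an unscheduled central result that day, the visit loses its value: the HemoCue is set aside and the central result is not assigned to the visit. Extra data turns an observed visit into a missing one.

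The row feeds the data set for a co-primary endpoint. A programmer who follows the table literally will impute a visit at which hemoglobin was measured, let that visit contribute twice to the evaluation-period mean, leave it out of by-visit summaries of observed scheduled values, and count the subject as partly imputed. If the visit is Week 52 and no other visit is missing, the gap is monotone, and the tipping-point analysis would apply a delta shift to a visit that has an observed result.

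**Working it through.** The SAP gives no figure to reproduce here. The check is to trace the label through the rules and then size the result.

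**1. Is the row an exception?** Ten legible rows of the table involve one or two value types. Seven of them contain a scheduled value:

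| Values on the date | Value used | Label |
|---|---|---|
| scheduled central | that value | Scheduled visit |
| scheduled HemoCue | that value | Scheduled visit |
| scheduled + unscheduled central | average | Scheduled visit |
| scheduled central + scheduled HemoCue | scheduled central | Scheduled visit |
| scheduled central + unscheduled HemoCue | scheduled central | Scheduled visit |
| scheduled + unscheduled HemoCue | average | Scheduled visit |
| unscheduled central + scheduled HemoCue | unscheduled central | **Unscheduled** |

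Six keep the visit. Only the last does not.

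**2. What follows from the label?** The value is unscheduled, so by Appendix 3 it fills no visit. The HemoCue is not used. The visit therefore has no scheduled value, and Section 7.1.2.5 imputes it.

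**3. Effect on one subject's mean.** There are seven scheduled visits in the evaluation period (Section 7.1.2.5). Let *m* be the mean of the other six, *u* the unscheduled central value and *i* the imputed value.

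- As written: (6*m* + *u* + *i*)/8.
- With the visit filled by *u*: *F* = (6*m* + *u*)/7.
- Since 6*m* + *u* = 7*F*, the difference is (7*F* + *i*)/8 − *F* = (*i* − *F*)/8, or 0.125 g/dL per 1 g/dL of deviation.

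Example with assumed values *m* = 10.5 and *u* = 9.5:

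- Filled: (63 + 9.5)/7 = 10.357.
- As written, *i* = 10.5: (63 + 9.5 + 10.5)/8 = 10.375, a shift of 0.018 g/dL.
- As written, *i* = 11.5: (63 + 9.5 + 11.5)/8 = 10.500, a shift of 0.143 g/dL.

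The extreme for a single imputation comes from the cutoffs of 6 and 15 g/dL in Section 7.1.2.5. With all observed values at 10.5, the shifts are (6 − 10.5)/8 = −0.56 and (15 − 10.5)/8 = +0.56 g/dL. The analysis pools 200 imputations, so a single draw at a cutoff overstates the effect.

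**4. Effect on an arm mean.** The SAP gives no frequency, so the following is assumed: a fraction *f* of one arm has one affected visit, and the average deviation is *d*. The shift is *f* × *d*/8.

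- *f* = 1%, *d* = 0.5: 0.01 × 0.5/8 = 0.0006 g/dL, or 0.08% of the 0.75 g/dL margin.
- *f* = 20%, *d* = 1.0: 0.20 × 1.0/8 = 0.025 g/dL, or 3.3% of the margin.

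**5. Per-protocol count.** Criterion 02 in Section 10.1.1 concerns subjects with fewer than 5 of 7 scheduled evaluable values. Its note 2 lets a HemoCue value stand in for a missing central one. Under note 2 the scheduled HemoCue can count; under the same-date table it has been set aside. The two places do not give the same answer.

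**The case against.** The strongest defence is that the row follows the SAP's own hierarchy. Section 10.6.3.1 turns to HemoCue only when the central value is missing, and here a central value exists for that date. A reader might infer that the general rule says the opposite of the table. It does not. Central-first supports the value chosen, and Appendix 3's default of not slotting unscheduled assessments is at least compatible with the label. This part of the defence stands in full for the value. It does not explain the label, because the neighbouring rows keep the visit whenever a scheduled measurement exists that day.

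A reader might also infer that the visit necessarily counts as missing for the per-protocol criterion. Note 2 in Section 10.1.1 prevents that conclusion, and subjects who meet a criterion only may be excluded, after blinded review. What remains is an ambiguity to be reconciled.

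A third tempting reading is that the observed result is lost from the co-primary analysis. It is not: the central value enters the evaluation-period mean as an unscheduled value. What is lost is the visit's status as observed, together with the HemoCue.

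Finally, the table does not itself say that the visit is imputed. That follows from reading it with Section 7.1.2.5 and Appendix 3. The opening lines of the subsection are only partly legible in the text at hand, so a qualifying sentence there cannot be excluded. The row itself is legible.

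**Conclusion.** The label in this row is a minor specification error. Applied as written, it causes a visit with a same-day measurement to be imputed and puts both an observed and an imputed value for that visit into the evaluation-period mean.

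The size is (imputed value minus filled mean)/8 for a subject with one affected evaluation-period visit. For an arm mean it is about 0.0006 to 0.025 g/dL under the assumed ranges of 1% to 20% of one arm and 0.5 to 1 g/dL, which have no support in the SAP beyond illustration. The combination needed is probably uncommon and the rule is the same in both arms, so the effect on the treatment difference should be very small. Nothing here suggests that the non-inferiority conclusion would change. The conclusion assumes that the table is programmed literally and that no unreadable text qualifies it.

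**What to change.** In the same-date table of Section 10.6.3.1, change the label of the row for unscheduled central plus scheduled HemoCue to Scheduled visit, and keep the central value. The visit then has one observed value, nothing is imputed for it, and the mean has seven terms instead of eight.

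State that the same rule governs the imputed-data summary in Section 7.1.2.5 and the count in criterion 02 of Section 10.1.1, so that both agree with note 2 there.

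The cost is one table cell, one clarifying sentence and about one line of code. No new data are needed.

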10.6.3.2. Iron Endpoints

Iro	n Endpoints				
Iro	Iron Medications				
•	 During the study, subjects may be receiving iron in multiple routes, including: IV iron Oral iron Other iron (including intramuscular, subcutaneous, and hemodialysis/dialysate) Note: The iron route categories above will be determined using the route on the 				
•	Prior/Concomitant Medication – Iron Therapy record. In addition, ferric citrate records recorded on the Prior/Concomitant Medication – Metabolic Bone Disease Therapy eCRF form will also be summarized as oral iron use.				
Ba	seline Iron Use				
•	The number and percentage of subjects in the following iron use categories at baseline will be summarized: IV iron use only Oral iron use only Other iron use only IV and oral iron use only IV and other iron use only IV and other iron use only Oral and other iron use only Oral and other iron use only IV, oral, and other iron use No iron use When determining baseline iron use, the gap factors mentioned below in the IV iron standardization algorithm will be applied to the end date for each iron record, and the baseline period of 16 weeks before the Randomization date until the day before the Randomization date will also be used.				
Sta	andardized IV Iron Dose (mg/week) to Determine Iron Management Action				
•	In order to compare between IV iron records, to determine the action taken with IV iron therapy in the 8 weeks following the date the IV management threshold was met, the dose of IV iron in each associated record will be standardized in terms of mg/month.				
•	 IV iron therapy concomitant medication records that occur or are ongoing during the 8 weeks following the date the IV management threshold was met (inclusive), will be selected and ordered by start and end date. If there is a record has a start date on the date the IV management threshold was met, and a prior record has an end date on the day before the IV management threshold was met, this prior record will be selected and considered as well. 				

200807

Iron En	dpoints
---------	---------

• The standardization will be carried out with the following formula:

• Standardized IV iron dose (mg/week) = IV iron drug dose (mg) * frequency

Note: Frequency defined as follows:

Frequency (from eCRF)	Frequency (for standardization formula)
2 times per week	2
3 times per week	3
4 times per week	4
5 times per week	5
BID	14
Once daily	7
One time dose	1
Every 12 Hours	14
Every 2 weeks	0.5
Every 4 weeks	0.25
Once a month	0.23
Once a week	1
TID	21

Standardized Baseline IV Iron Dose (mg/month)

- In order to calculate the baseline average monthly IV iron dose, the dose of IV iron will be standardized to obtain a continuous single unit IV iron dose in terms of mg/month for the period from 16 weeks before the Randomization date to the day before the Randomization date.
- IV iron therapy concomitant medication records that occur or are ongoing during the period from (the Randomization date – 16 weeks) to the Randomization date will be selected and ordered by start and end date.
- The standardization will be carried out with the following formula:
 - Standardized IV iron dose (mg/week) = IV iron drug dose (mg) * frequency

Note: Frequency and Gap Factors defined as follows:

Frequency (from eCRF)	Frequency (for standardization formula)	Gap Factor
2 times per week	2	2.5 days
3 times per week	3	1.33 days
4 times per week	4	0.75 day
5 times per week	5	0.4 day
BID	14	0 days
Once daily	7	0 days
One time dose	1	n/a
Every 12 Hours	14	0 days
Every 2 weeks	0.5	13 days
Every 4 weeks	0.25	27 days
Once a month	0.23	29 days

200807

0	nce a week	1	6 days
TI	D	21	0 days
		1	-
the f	frequency of the record is	s not 'one time dose', then duration	is calculated as follow
0		lication record start date \geq Randon	nization date, the dura
	the record is 0.		
0		lication record end date + gap facto	or < (Randomization d
	16 weeks), the duratio		
0		lication record end date + gap facto	
	,	d is ongoing, the duration of the re-	cord will be calculated
	Stop Date – Start Date		ation record start date
		be the latest of (concomitant medic ation date – 16 weeks).	
		be the earliest of (concomitant med	dication record stop de
		I the day before randomization).	
tho f	frequency of the record is		
0		tion record start date < Randomizat	tion date - 16 weeks o
0		concomitant medication record sta	,
	record is 0.		
0		-16 weeks ≤ concomitant medicati	on record start date <
Ũ	Randomization date, t		
		r standardization formula) = 1	
	 Duration = 7 c 		
ne to	tal dose for each IV iron	record will be: Standardized dose*	duration/7 days
weig	ghted mean will then be u	used to obtain the baseline monthly	VIV iron dose:
lean	baseline monthly IV iron	dose = [(IV iron total dose _{Record 1}) +	+ (IV iron total dos
]/[(1	6* 7)/30.4375 days].		
dardi	zed IV Iron Dose (mg/n	nonth) from Randomization to W	eek 52
ו ord	er to calculate the average	e monthly IV iron dose from Rando	omization to Week 52,
		lized to obtain a continuous single	
-	•	he Randomization date to the Wee	
ubjec		fore their first RBC or whole blood t	
		o are randomized but never treated	
.	• ·	V iron from Randomization to Weel	
		edication records that occur or are ion date – 16 weeks to the Week 5	
	rdered by start date and		
	•	ried out with the following formula:	
0		ose (mg/week) = IV iron drug dose	(ma) * frequency
0			(mg) nequency
Fred	uency and Gap Factors	defined as follows:	
	equency (from eCRF)	Frequency	Gap Factor
		(for standardization formula)	-
2	times per week	0	0 E dava

2

2.5 days

2 times per week

200807

Iron E	ndpoints		
	3 times per week	3	1.33 days
	4 times per week	4	0.75 day
	5 times per week	5	0.4 day
	BID	14	0 days
	Once daily	7	0 days
	One time dose	1	n/a
	Every 12 Hours	14	0 days
	Every 2 weeks	0.5	13 days
	Every 4 weeks	0.25	27 days
	Once a month	0.23	29 days
	Once a week	1	6 days
	TID	21	0 days

• If the frequency of the record is not 'one time dose', then duration is calculated as follows:

 If the concomitant medication record start date > earliest of (treatment stop date + 1 and Week 52 visit date), the duration of the record is 0.

• If the concomitant medication record end date + gap factor < Randomization date, the duration of the record is 0.

 o If the concomitant medication record end date + gap factor ≥ Randomization date or the record is ongoing, the duration of the record will be calculated as Stop Date – Start Date +1 day where:

- Start date will be the latest of (concomitant medication record start date, randomization date, treatment start date).
- Stop date will be the earliest of (concomitant medication record stop date + gap factor, first transfusion date (RBC or whole blood), treatment stop date + 1, and the Week 52 visit date).
- If the frequency of the record is 'one time dose', then:
 - If concomitant medication record start date < treatment start date, or if earliest of (first transfusion date (RBC or whole blood), treatment stop date +1 and Week 52 visit date)
 < concomitant medication record start date, then duration of the record is 0.
 - o If latest of (Randomization date, treatment start date) ≤ concomitant medication record start date ≤ earliest of (first transfusion date (RBC or whole blood), treatment stop date + 1 and Week 52 visit date), then:
 - Frequency (for standardization formula) = 1
 - Duration = 7 days
- The total dose for each IV iron record will be: Standardized dose*duration/7 days
- A weighted mean will then be used to obtain the monthly IV iron dose from Randomization to Week 52:

Mean monthly IV iron dose from Randomization to Week 52 while on treatment = $[(IV \text{ iron total } dose_{Record 1}) + ... + (IV \text{ iron total } dose_{Record n})] / {[earliest of (treatment stop date + 1, Week 52 Visit Date) - treatment start date + 1] / 30.4375 days}.$

200807

Iron Endpoints

Standardized Monthly IV Iron Dose (mg/month) from Week 28 to Week 52 (EP Average Monthly IV Iron Dose)

 In order to calculate the average monthly IV iron dose from Week 28 to Week 52, the dose of IV iron will be standardized to obtain a continuous single unit IV iron dose in terms of mg/month for the period from the Week 28 visit date to the Week 52 visit date while the subject is on treatment and before their first RBC or whole blood transfusion.

- Note: Subjects who are randomized but never treated, who have a RBC or whole blood transfusion, or who permanently discontinue randomized treatment on or before the Week 28 visit date will not have a value for average monthly IV iron from Week 28 to Week 52.
- IV iron therapy concomitant medication records that occur or are ongoing during the period from the subject's Week 24 visit date to the Week 52 visit date will be selected and ordered by start date and end date.
- The standardization will be carried out with the following formula:
 - Standardized IV iron dose (mg/week) = IV iron drug dose (mg) * frequency

Note: Frequency and Gap Factors defined as follows:

Frequency (from eCRF)	Frequency (for standardization formula)	Gap Factor
2 times per week	2	2.5 days
3 times per week	3	1.33 days
4 times per week	4	0.75 day
5 times per week	5	0.4 day
BID	14	0 days
Once daily	7	0 days
One time dose	1	n/a
Every 12 Hours	14	0 days
Every 2 weeks	0.5	13 days
Every 4 weeks	0.25	27 days
Once a month	0.23	29 days
Once a week	1	6 days
TID	21	0 days

- If the frequency of the record is not 'one time dose', then duration is calculated as follows:
 - If the concomitant medication record start date > earliest of (treatment stop date + 1 and Week 52 visit date), the duration of the record is 0.
 - If the concomitant medication record end date + gap factor < Week 28 visit date, the duration of the record is 0.
 - If the concomitant medication record end date + gap factor ≥ Week 28 visit date or the record is ongoing, the duration of the record will be calculated as Stop Date Start Date +1 day where:
 - Start date will be the latest of (concomitant medication record start date, and

Iron Endpoints	
•	
 the Week 28 visit date). Stop date will be the earliest of (concomitant medication record stor gap factor, first transfusion date (RBC or whole blood), treatment s 1, and the Week 52 visit date). 	
 If the frequency of the record is 'one time dose', then: If concomitant medication record start date < Week 28 visit date, or if earlied transfusion date (RBC or whole blood), treatment stop date + 1 and Week date) < concomitant medication record start date, then duration of the record If Week 28 visit date ≤ concomitant medication record start date ≤ earliest transfusion date (RBC or whole blood), treatment stop date +1 and Week date), then: 	52 visit ord is 0. of (first
 Frequency (for standardization formula) = 1 Duration = 7 days 	
 The total dose for each IV iron record will be: Standardized dose*duration/7 days A weighted mean will then be used to obtain the monthly IV iron dose from Week 2 52: 	8 to Week
Mean monthly IV iron dose from Week 28 to Week 52 while on treatment = [(IV iron total dose _{Record 1}) + + (IV iron total dose _{Record n})] / {[earliest of (treatm date + 1, Week 52 Visit Date) – Week 28 Visit Date +1]/30.4375 days}.	ent stop
Iron Use by Quarter	
 The number and percentage of subjects in the following iron use categories defined will be summarized by quarters listed below for Average Quarterly IV Iron Dose: IV iron use only Oral iron use only Other iron use only IV and oral iron use only IV and oral iron use only IV and other iron use only Oral and other iron use only Oral and other iron use only IV, oral, and other iron use only IV, oral, and other iron use No iron use When determining iron use by quarter, the gap factors mentioned in the IV iron star algorithm will also be applied to the end date for each iron record. Although baseline iron use is defined based on a period of 16 weeks, it will also be 	ndardization
summaries of iron use by quarter.	
Average Quarterly IV Iron Dose	
 The standardized IV iron (mg/month) dose will be summarized by quarters, where the be defined using study visits as follows: Baseline 	quarters will
 For summaries of on & off treatment IV iron dose: Quarter 1 = [Randomization date – Week 12) For summaries of on-treatment IV iron dose: 	
 Quarter 1 = [Treatment start date + 1 – Week 12) Quarter 2 = [Week 12 – Week 24) 	

200807

2000
Iron Endpoints
 Quarter 3 = [Week 24 – Week 36) Etc.
• To determine the planned start date and end date of quarters, the visit end date (from the SV domain) will be used. If there is not a corresponding visit, or if the subject is missing that visit the planned visit date (Randomization date + 7*x) will be used, where x is the scheduled wee (e.g., Week 24, x = 24).
 A subject's quarterly average IV iron dose will end at the earliest of the following: For summaries of on & off treatment IV iron dose: death date, study completion/withdrawal date, and the planned quarter end date. For summaries of on-treatment IV iron dose: death date, first transfusion (RBC o whole blood), study completion/withdrawal date, treatment stop date + 1, and the planned quarter end date.
 The standardization algorithm for IV iron described earlier in the table will be used to determi the standardized IV iron dose (mg/month) during each quarter. Although the standardized baseline IV iron dose is defined based on a period of 16 weeks, it will also be included in summaries of average quarterly IV iron dose.
Reduction in IV Iron Supplementation
 A reduction in IV iron supplementation relative to baseline occurs when Baseline average monthly IV iron > EP average monthly IV iron, when both baseline IV iron and EP average monthly IV iron are non-missing.
TIBC
 TIBC will be calculated automatically by the central laboratory using: TIBC = UIBC + total iron
TSAT
 TSAT will be calculated automatically by the central laboratory using: TSAT = 100 * (Serum Iron/TIBC)
Average Quarterly TSAT and Ferritin
 The average TSAT and Ferritin values will be summarized by quarters, where quarters will be defined as they are for Average Quarterly IV Iron Dose, with the following exception: Baseline average quarterly ferritin and TSAT will take the average of all available records before or on randomization ferritin and TSAT values.
Note: any unscheduled values falling within these quarters will be used in the calculation of the quarterly average value.
Meeting Iron Management Criteria
 Iron therapy will be administered if at any visit: Ferritin ≤ 100 ng/mL and/or TSAT ≤ 20% All iron must be stopped if at any visit: Ferritin > 800 ng/mL and TSAT >20%, or TSAT > 40%
Subjects meeting iron management criteria requiring starting and stopping of iron administration of the same day:

• Ferritin \leq 100 ng/mL and TSAT > 40%

200807

